Trial Protocol and Statistical Analysis Plan

Final protocol
Final statistical analysis plan
Summary of statistical analysis plan changes

Abstract

Due to the widespread use of social media, behavioral health providers have increasingly interacted and/or reviewed patients social media activity. This project seeks to harness social media data in a clinical mental health setting by partnering with both patients and their providers. We will work with these two groups to create social media and digital data dashboard that can be shared before or during clinical encounters. Our objective is to explore and evaluate how a patient-centered personalized social media summary dashboard could be used in a behavioral health therapy session to improve depressive symptoms and anxiety and if a social media dashboard improves patient and provider therapeutic alliance and engagement.

Background

Last year, approximately 4 million adults and 2 million adolescents received any mental health care. Mental health treatment can be highly effective in reducing symptoms and improving functioning of people in psychiatric distress. The nature of the clinical encounter is such that there can be a disconnection between it and the rest of the patients life. That is, patients may meet for 50 minutes with their therapist once a month or in rarer cases once a week. The therapist relies almost solely on patient report of thoughts, mood and behavior, and the events that preceded and followed them. Recall bias, social desirability bias, and the nature of the therapeutic relationship all may affect the accuracy, completeness and quality of the information the patient shares with his/her therapists. Poor accuracy of this communication then can affect the quality and outcomes of therapy. In some cases, changes in mood and adverse life-threatening events may be missed. It is not uncommon for patients to share written communication (e.g. a letter) with their therapist that occurred between the patient and a third party. These artifacts can be helpful to the therapist in assessing the patients mental state at the time of the communication and in providing feedback and advice regarding relationships. It is increasingly likely that this written communication will be electronic. Electronic communication, including emails, texts and social media, are now ubiquitous in our society. Approximately 2.4 million emails are sent per second, 22 billion texts per day. More than 79% of US adults actively use Facebook and use across other platforms like Twitter and Instagram is growing exponentially. These communications may offer an exciting way to support the effectiveness of mental health treatment. They can offer insight into patients mood, thoughts, lifestyle, and behavior that may not be available otherwise. This area of study raises several questions such as: How can clinicians best make use of the huge volume of raw, unstructured data that are available through social media and electronic communication (i.e. texts, emails)? How do therapists incorporate this data in the most productive way, without disrupting the therapeutic process? We strongly believe that there will be value in linking individual level information on social media to health outcomes and behavior; a better understanding actual patient willingness to share online data output could help to significantly improve our understanding of applications of digital data for health research. Our assumption is that ultimately this information will have tremendous utility for supporting more measurement-based care. In our ongoing work at Penn (Penn IRB 819442) we have enrolled over 6000 patients to share access to social media and EMR data. Of individuals who use social media and are willing to participate in research, approximately 85% of patients agree to share social media and EMR data. To date we have used this data to predict differences in medical diagnoses (e.g. hypertension, depression). We have also generated patient dashboards of general information about their health and social media use (Penn IRB: 819442)

January 6, 2022

Overall Objectives

Our objective is to explore and evaluate how a patient-centered personalized social media summary dashboard could be used in a behavioral health therapy session to improve depressive symptoms and anxiety and if a social media dashboard improves patient and provider therapeutic alliance and engagement.

Aims

Primary Aims

Determine the impact of incorporating digital data and electronic communication dashboard in behavioral health treatment on patient reported health-related quality of life (SF-36) compared to usual care

Secondary Aims

Determine the impact of incorporating digital data and electronic communication dashboard in behavioral health treatment on patient-reported depressive (PHQ-8) and anxiety (GAD-7) symptoms compared to usual care.

Determine the impact of incorporating digital data and an electronic communication dashboard in behavioral health treatment on therapeutic alliance (WAI-SR) compared to usual care.

Determine the impact of incorporating digital data and an electronic communication dashboard in behavioral health treatment on the CIS checklist compared to usual care.

Primary Outcome Variable

Examine self-report of health-related quality of life (SF-36), specifically mental health (vitality, social functioning, role-emotional and emotional well-being) under the intervention and control conditions and the change over the study period.

Secondary Outcome Variables

Examine depression (PHQ-8), anxiety (GAD-7), and therapeutic alliance (WAI-SR) under the intervention and control conditions and the change over the study period.

Examine the therapeutic alliance (WAI-SR) and frequency digital data and electronic communication is discussed in therapy (CIS checklist) under the intervention and control conditions and the change over the study period.

Study Design

Phase Not applicable

Design

A randomized controlled trial for patients and their mental or behavioral health provider from Penn Medicine, Hall Mercer, and/or Horizon House or greater Philadelphia mental health practices and clinics to investigate the impact of incorporating digital data and electronic communication dashboard in behavioral health treatment session. Patient and provider participants will be randomized to receive the

treatment (having a digital health dashboard to be used at least two therapy sessions over a 2-month

NCT04011540

January 6, 2022

period) or the control (usual care). Participants who consent to share their social media and digital data, we will use a Facebook application previously designed for this purpose, Instagram API to access data, and Google take-out file. Patients will visit on an incognito browser https:// donate.centerfordigitalhealth.upenn.edu to safely and securely download social media and digital data. The data collection platform was reviewed by Penn Medicine IS team, please approval attached to this submission. Participants who agree to share their social media data will log in to their own Facebook account and download an application. When users first activate the application, they grant the right to researchers to access the information contained in their Facebook profiles. They will then be directed to a Facebook application called Penn Image Station that was designed for the purposes of this study. The Penn Image Station application will gather information from their Facebook public profile, status updates, personal description, and likes. The application will not affect their usual use of Facebook nor will it post to their page. Facebook data will be collected historically (all data that ever existed) and prospectively for 60 days. If they share their Google take-out, they will download a zip file of their google searches and YouTube activity. Google take-out data is only historical and retrospective. If the participant shares their Instagram posts, they will be directed to an Instagram application called Penn Social Mediome. They will read a brief statement, either agree or disagree with the statement, and then log on to their Instagram account. Their Instagram posts and photos will be extracted by the Penn Social Mediome application and will be collected historically and 60 days prospectively. No passwords would be collected by the study team. Patient participants will be asked to download AWARE, a free app on their smartphone. AWARE is an Android framework dedicated to instrument, infer, log and share mobile context information, for application developers, researchers and smartphone users. AWARE captures hardware-, software-, and human-based data. The data is then analyzed using AWARE plugins. AWARE is compatible on iPhone, Android, and Google phones. The use of the AWARE app in Penn research projects has been previously approved IRB #83254, The Networks of Daily Experiences (NODE) Study: Within-Person Change in Curiosity and Implications for Well-Being, (PI: [name]). When subjects download the application, they will enter a Study ID number, which will be used to link their data with survey responses from Way to Health unique ID number. AWARE. Aware data will be included for only 60 days prospectively. This application and methodology has been previously used by investigators in this protocol for research within the World Well Being Project at the Positive Psychology Center at the University of Pennsylvania (prior Penn IRB protocols #816091, 813820, 819442, 824493). After completing the survey, donating their digital data, and downloading AWARE app, participants will be enrolled in Way To Health, a HIPAA compliant research infrastructure to receive complete day 60 and day 90 surveys. Patient participants will be contacted up to 5 times to complete each survey. If patient participants are randomized to the intervention arm, they will be prompted to complete text message prompts before each therapy session. The text message prompts entail appointment reminders and how to contribute screenshots to populate their electronic communication and digital data dashboard. The informed consent documents outline how patients will not contribute any PHI data through the Way to Health texting platform and how to only respond to the text message prompts. Additionally, if patients are randomized to the intervention arm, they will also be coached and briefed on text message confidentiality and privacy best practices. After approximately seven days from when digital data is received, the patients randomized to the intervention group will receive their first electronic communication and digital data dashboard summarizing findings from their historical social media, google take-out, and AWARE data. For example, electronic communication and digital data dashboard will include information such as average amount of time spent on smartphone during 12am-4am, physical activity callouts (i.e., most and least moved days), and most commonly used words on Google

NCT04011540 January 6, 2022

search and YouTube. If patients want to share additional digital data, they will text in screenshots via Way to Health (safety and privacy measures are noted above). The provider participants randomized to the intervention arm will receive a brief training on the dashboard components and safety and privacy practices. Providers will watch a 3-minute video explaining how they will receive the dashboard each week and what data is being included. For example, the video breaks down each module. For the latenight phone activity module, it states late night phone activity is the amount of time your patients phone screen is on. The amount of time one spends on their phone is relative to each person and there is no right or wrong amount of time. No specific post or activity will be highlighted on the dashboard; rather trends and summaries will be displayed. The research team will work closely with the patient participant and their provider to distribute the dashboard before the patients next behavioral health appointment. The provider participants randomized to the intervention arm, will be emailed their patients dashboard via Penn +Box, a cloud-based collaboration service for securely managing and sharing files and folders within the Penn community and externally. Penn+Box also ensures that University data and intellectual property are securely protected. In addition, Penn Medicine providers can elect to have the dashboard delivered to their office, [name], each morning at 9:30 am or before they see their patient. Dashboards will be delivered in a sealed envelope and delivered to the clinic front desk person or directly to the therapist. There will be no medical advice or evaluation will be included in a dashboard. If a dashboard is unable to be generated, the patient will be prompted to bring their smartphone into session and to discuss something from it, if applicable.

Method for Assigning Subjects to Groups

Patient participants will be randomized after they donate digital data sources and complete baseline survey. We will use Way to Health's computer-generated algorithm to randomize patient participants in block sizes of 2, 4, and 6. Patient participants will be randomly assigned to control (usual care) or experimental group (use of digital health dashboard over the 2-month study period). Study assignments will be stored in Way to Health. The study will be single-blinded. The research team will know which participants are receiving the active medication or treatment and which are not. The participants will not be blinded to their assignment. Provider participants will be enrolled in the arm of their patient. There is possibility that provider participants are exposed to the intervention for 1 patient and usual care for another, despite this limitation, we will control for contamination in analyses. The study biostatistician will determine when to unblind the study.

Study Duration

This entire study will last approximately 2 years. Randomized controlled trial participants, both patient and providers, involvement is approximately 3 months, 90 days.

Facilities

Our team is diverse and multi-disciplinary. [name] is an Associate Vice President at Penn Medicine and an Associate Professor of Emergency Medicine at the University of Pennsylvania. She has secondary appointments in the Department of Internal Medicine and Department of Anesthesia and Critical Care. [name] is a Professor of Psychiatry at the University of Pennsylvania, where he directs the Center for Mental Health Policy and Services Research. He also is Vice-Chair for Research. He has a 30-year history of partnering with mental health providers in Philadelphia to improve care. [name] is a postdoctoral researcher and his research leverages large-scale social media image and text data to model social health outcomes and psychological traits. [name] is an Assistant Professor of Psychology in Psychiatry in the Perelman School of Medicine, University of Pennsylvania.

NCT04011540 January 6, 2022

Patient Inclusion - Between 18-65 years of age - Primarily English speaking (for language analysis) Willing to share at least one digital data source this includes Facebook, Google searches, YouTube searches, or screen time by downloading a free application (app) on their smartphone. - Has a mental or behavioral health provider and currently enrolled in mental or behavioral therapy - Attends therapy at least once a month and expected to remain in therapy for the next three months - Willing to share social media dashboard with their behavioral health provider - Able to provide informed consent - Regular activity viewing and posting on social media sites, defined as once a month posting - Owns an Smartphone - Willing to download and keep an app on their phone for 3 months

Provider Inclusion - 18 years of age or older - Primarily English speaking - Provides therapy for patient participant - Willing to review a summarized social media dashboard before or in a therapy session Intends to complete post therapy weekly surveys

Key Exclusion Criteria

Patient Exclusion - Under 18 years of age - Non-English speaker - Patient is in severe distress, e.g. respiratory, physical, or emotional distress - Patient is intoxicated, unconscious, or unable to appropriately respond to questions - Not currently enrolled in therapy or does not attend at least monthly - Not expected to remain in therapy for the next three months - Not a regular social media poster, or does not use Facebook, Instagram and/or not willing to share - Unwilling to share social media summary dashboard with behavioral health provider - Patient with diagnosed psychosis -Does not own a smartphone - Unwilling to download and keep an app on their phone for 3 months.

NCT04011540 January 6, 2022

Provider Exclusion - Under 18 years of age - Non-English speaker - Not a registered behavioral health provider - Not provider for a RCT participant - Unwilling to review a social media summary dashboard before or during in a therapy session with RCT participant - Unwilling to complete weekly surveys

Subject Recruitment

Target Population

The target population is participants 18 years and older, primarily English speaking, a self-report of anxiety and/or depression, seeking mental health therapy at outpatient Penn Medicine clinics, Hall Mercer, and/or Horizon House; Center for Cognitive Therapy, Center for the Treatment and Study of Anxiety, Department of Psychiatry at the Perelman School of Medicine, or greater Philadelphia mental health practices and clinics, or public/private mental health centers/clinics in the continental U.S. Patient patients are expected to attend therapy sessions at least once a month for 3 months. Provider Participant, the target population is a provider who provides therapy sessions for a patient participant. Patient Participant The target population is participants 18 years and older, primarily English speaking, a self-report of anxiety and/or depression, seeking mental health therapy at outpatient Penn Medicine clinics, Hall Mercer, and/or Horizon House; Center for Cognitive Therapy, Center for the Treatment and Study of Anxiety, Department of Psychiatry at the Perelman School of Medicine, or greater Philadelphia mental and Study of Anxiety, Department of Psychiatry at the Perelman School of Medicine, or greater Philadelphia mental health practices and clinics and attends therapy sessions at least once a month for 3 months. Provider Participant, the target population is a provider who provides therapy sessions for a patient philadelphia mental health practices and clinics and attends therapy sessions at least once a month for 3 months. Provider Participant, the target population is a provider who provides therapy sessions for a patient philadelphia mental health practices and clinics and attends therapy sessions at least once a month for 3 months.

Accrual

We will draw upon our working relationships with our various recruitment sites. The randomized controlled trial will be powered on SF-36 change in the patient participant. We used PASS to calculate the minimum detectable score difference required for over 80% power assuming a type I error rate of 0.05. We assumed 50 in each arm. We used the test for two means in a repeated measures ANCOVA. We assumed the correlation between repeated measures to be 0.60 (r2=0.36). The following values were used in the sample size calculations: SF36 Norms Mental Component Summary (MCS): mean = 50; sd = 10 Vitality: mean = 60.9; sd = 21.0 Social Functioning: mean = 83.3; sd = 22.7 Role-Emotional: mean = 81.3; sd = 33.0 Mental Health: mean = 74.7; sd = 18 Table: Minimum detectable score differences Sample Size 50 in each arm MCS 5 Vitality 10 Social Functioning 11 Role-Emotional 15 Mental Health 9 We aim to enroll 115 participants in a randomized controlled trial, with the anticipation that there will be 15% attrition.

Patient Subject Recruitment

We will identify participants across several settings: inpatient and outpatient Penn Medicine clinics (e.g., Emergency Department, Internal Medicine, Center for Cognitive Therapy, PIC, LGH mental health clinics), flyers at [name] and Penn Medicine iConnect (Use of Patient Electronic Communication in Psychiatric Evaluation and Treatment, Study Identifier: 831246), Google ads, Facebook ads, ResearchMatch.org, and provider referrals. Interested patient participants will be directly approached by a research assistant (RA) via email, telephone or BlueJeans. Patients who are receiving care in these settings will receive a digital or printed flyer about the opportunity to participate in a research study. In outpatient units, Ras or AAs will meet regularly with the nursing coordinator, office manager, charge nurse, nurse/ physician team to determine the daily census and appropriateness of approaching patients. If necessary, research assistants will also communicate directly with patients providers (physicians, residents or nurses) to determine whether it is appropriate to approach the patient.

NCT04011540 January 6, 2022

Potentially eligible patients will be approached via email, telephone or BlueJeans to verify they meet all inclusion criteria and will then be asked to participate.

Compensation

Patient participants will receive a \$50 Greenphire clincard at baseline once they complete the baseline survey, download AWARE, and donate digital data. At day 60, once they complete the day 60 survey and interview, \$100 will be loaded on their Greenphire clincard. At day 90, patients will receive another \$50 if they complete a survey. Provider participants in both arms will receive \$50 a month on a Greenphire clincard or allocated to their clinic for completing post-therapy survey and the day 60 and 90 monthly survey. At day 60, providers will be asked to complete a debriefing interview. Provider participants will receive additional \$50 loaded to their Greenphire clincard or allocated to their clinic if they complete 80% of the CIS checklist surveys, which is approximately 7 of 8 surveys

Study Procedures

Consent Process

Potentially eligible patients will be approached to verify they meet all inclusion criteria and will then be asked to participate. A RA will approach participants and explain the study in brief via email, telephone, BlueJeans or in-person. Subjects will be asked to confirm whether they will share or not share their Facebook and or Instagram data with health researchers as described in this protocol. Patients willing to share will complete a consent form. All consents will be obtained in a secure and private area on UPenns campus or University city or online. All efforts will be made to ensure that patients understand that participation is voluntary and will not affect their care or treatment in any way. The RA will obtain informed consent using the attached paper consent form or online. The RA will describe the study in detail, including the survey and the use of the Facebook/Instagram application/ plugin to extract their posts for language and photo analysis, AWARE app, and google search download instructions. The participant may refuse to answer any questions for any reason, can skip any question, and can stop participation at any time. Subjects may uninstall the Facebook/Instagram app to stop sharing their posts at any time. Or they may contact the research team as described in the consent to have their information deleted and permanently removed from the study database. The verbal consent form indicates that the participant may refuse to answer any questions for any reason, can skip any question, and can stop at any time. The research presents no more than minimal risk of harm to subjects and involves no procedures for which written consent is normally required outside of the research context. All study activities will occur in-person during enrollment or on the Way to Health, HIPAA Compliant platform, stored on PMACS. The research presents no more than minimal risk of harm to subjects and involves no procedures for which written consent is normally required outside of the research context. The study is not intervening or currently changing patient care. We will tell participants that we are not using the data for diagnostic purposes and the identifying information we will collect includes name, age, race, gender, and email address, cell-phone number, home address, and social security number.

Minimal Risk

This study is minimal risk and there are no known risks associated with participation in this research beyond those of everyday life.

Analysis Plan

Stata, SAS, and NVivo software will be used for analyses. All data will be summarized using descriptive statistics (mean or median, standard deviation, or interquartile range for continuous variables,

NCT04011540 January 6, 2022

frequencies for categorical variables) and graphical techniques (histograms, scatterplot) as appropriate. Standard summary descriptive statistics to be used to analyze data from the survey. We will extract data from social media and wearable device platforms and aggregate to develop dashboards. Qualitative analysis using grounded theory will be applied for the focus group discussion, interviews, and openended survey questions. We will conduct an intent to treat (ITT) analysis. The ITT analysis will include all randomized patients in the groups to which they were randomly assigned, regardless of their adherence with the entry criteria, regardless of the treatment they actually received, and regardless of subsequent withdrawal from treatment or deviation from the protocol. Baseline demographic and clinical characteristics will be reported as frequency and percent for categorical variables and median and interguartile range (IQR) for continuous variables. We will compare baseline characteristics between intervention and control arms using t-tests for continuous variables and chi-squared tests for categorical variables. The goal of these comparisons will be to determine if the two arms are balanced on baseline variables after randomization. For the primary analysis, we will use linear mixed effects models to assess whether average of SF 36 scores over study follow-up differ between the two arms. We will use a random effect to account for the correlation in repeated outcome measures over time within participants. We will also account for correlation in outcome measures by therapist (as participants will be randomized within therapist), by including additional random effects to account for the nesting of patients within therapists. The primary parameter of interest will be a binary indicator for treatment arm assignment. Models will also include a variable for time of measurement. Baseline covariates that are found to be unbalanced between arms may be adjusted for in the model if they were deemed to be potential confounders a priori to adjust for potential confounding and for efficiency gain. We will use all available SF 36 scores on eligible patients from randomization through the last observation. An advantage of the linear mixed effects model is that it is robust to missing outcome measures as long as the missingness mechanism is missing at random (MAR). Patterns of missingness will be assessed carefully and multiple imputation will be used if deemed appropriate. Robust (empirical) standard errors will be used. A p0.05 will be deemed statistically significant but emphasis will be placed on point estimates and confidence intervals. In secondary analysis, we will also include an interaction term between intervention arm and time in order to assess whether the intervention affects the slope of SF 36 scores over time. We may also consider testing interactions between intervention and sex or other important covariates to test if there are differences in the effect of intervention by pre-specified subgroups. We will use a similar approach to evaluate secondary outcomes; however, depending on the distributional form of the secondary outcome, we will use a generalized mixed effects model with the appropriate functional forms for the distribution family and link function.

This study was deemed minimal risk and there were no stopping guidelines.

Subject Confidentiality

The research team will exercise extreme caution with identifiable private information. Patients are donating historical and prospective for 60 days digital data. We are not viewing any digital or social media data in real-time. Patients randomized to the intervention arm will receive weekly messages from Way to Health. In the patients informed consent, they are instructed and agree by signing the document that they will not disclose personal health information (PHI) on the Way to Health texting platform and only respond to the text message prompts. When patient participants (both control and intervention) text into the Way to Health or complete a survey, the research team will receive email notification immediately. The research team is instructed to review the message within 1-4 hours of delivery, Monday through Friday, 8 am to 5pm. The line will be closed on Saturday and Sunday however patient

NCT04011540 January 6, 2022

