
Amendments to the Statistical Analysis Plan

All amendments to the original SAP were made prior to unblinding of the data analyst and prior to access to outcome data.

Based on covariate balance between the intervention arms, we amended our original statistical analysis plan. In addition, we originally anticipated enrolling 20-30 therapist participants with several patients nested within each therapist. This would have necessitated the accounting for clustering within therapist using random effects. However, we enrolled 69 therapist participants with cluster sizes that were very small, with most therapists treating 1-2 patients. Hence, as our primary analysis, we conducted an unadjusted paired t-test (rather than our originally proposed linear mixed model) to compare mean changes on our primary outcomes from baseline to 60-day. As a secondary analysis, we did conduct a linear mixed effects model exactly as proposed in the original SAP. These results were nearly identical to the unadjusted paired t-test and would not change our conclusions. In addition, we conducted a complete case analysis as our primary analysis. After assessing patterns of missingness and determining that missing at random is a plausible mechanism in this study, we conducted multiple imputation. Again, our imputed results were nearly identical to the complete case analysis with identical conclusions.

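### The stated detectable differences belong to a baseline-adjusted ANCOVA; the declared primary t-test of change has 71% to 79% power at them, not over 80%, at the plan's own correlation of 0.60

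*Combined protocol and SAP*

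**What the plan says.** The Accrual section states the target: "The randomized controlled trial will be powered on SF-36 change in the patient participant". It then gives the method: "We used PASS to calculate the minimum detectable score difference required for over 80% power assuming a type I error rate of 0.05", with 50 patients per arm. The test and the correlation follow: "We used the test for two means in a repeated measures ANCOVA. We assumed the correlation between repeated measures to be 0.60 (r2=0.36"). The resulting table lists 5 (MCS), 10 (Vitality), 11 (Social Functioning), 15 (Role-Emotional) and 9 (Mental Health). On enrolment it says: "We aim to enroll 115 participants in a randomized controlled trial, with the anticipation that there will be 15% attrition".

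The Analysis Plan and the Original Statistical Analysis Plan proposed a linear mixed model for the average SF-36 score over follow-up. It has terms for arm and time. Baseline covariates enter only if found unbalanced and judged confounders beforehand, and baseline SF-36 is not named.

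The Amendments to the Statistical Analysis Plan replace that model as primary with "an unadjusted paired t-test (rather than our originally proposed linear mixed model) to compare mean changes on our primary outcomes from baseline to 60-day". They add that "we conducted a complete case analysis as our primary analysis", and state: "All amendments to the original SAP were made prior to unblinding of the data analyst and prior to access to outcome data". Of the mixed model, now secondary, they report: "These results were nearly identical to the unadjusted paired t-test and would not change our conclusions".

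**The concern.** The only power statement in the documents describes a test that is not the declared primary. An ANCOVA uses the baseline score to remove part of the outcome variance. A t-test of change subtracts the baseline in full, which is less efficient whenever the correlation is below 1. With the same patients and the same correlation, the differences detectable with 80% power must therefore be larger than the table says.

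A reader who judges the result against the table would credit the primary test with sensitivity that it lacks under the plan's own assumptions. The choice also widens the confidence intervals, on which the plan says it will place its emphasis.

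A second problem is the word paired. Taken literally, a paired t-test compares visits within patients and does not compare the arms.

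**Working it through.** **Inputs (Accrual section).** SDs 10, 21.0, 22.7, 33.0 and 18; n = 50 per arm; alpha 0.05; r = 0.60.

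**Assumptions.** Two-sided testing (sidedness is not stated), equal variances over time, complete data, and the paired test read as a two-sample t-test of within-patient change. Every change-score figure below depends on that reading.

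**Variance factors.**
- ANCOVA, one follow-up score with baseline as covariate: 1 − r² = 1 − 0.36 = 0.64, so the working SD is 0.80 × SD.
- Change score: 2(1 − r) = 2 × 0.40 = 0.80, so the working SD is 0.894 × SD.

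**Formula.** The standard error is SD × √factor × √(2/50) = SD × √factor × 0.2. The difference detectable with 80% power is about 2.83 standard errors (noncentral t; the normal approximation gives 2.80).

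**Reproducing the plan's table.** For MCS under ANCOVA: 10 × 0.80 × 0.2 = 1.60, and 2.83 × 1.60 = 4.53, which rounds up to 5. All five values match when rounded up. Power at the stated differences is then 80% to 87%, so the claim of over 80% is true for ANCOVA.

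**Applying the declared primary test.** For MCS: 10 × 0.894 × 0.2 = 1.79, and 2.83 × 1.79 = 5.06.

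| Scale | Stated | ANCOVA detectable | ANCOVA power at stated | Change detectable | Change power at stated | n per arm for 80% (change) | r needed for 80% (change, 50 per arm) |
|---|---|---|---|---|---|---|---|
| MCS | 5 | 4.53 | 87.2% | 5.06 | 79.0% | 52 | 0.61 |
| Vitality | 10 | 9.51 | 83.8% | 10.63 | 75.0% | 57 | 0.65 |
| Social Functioning | 11 | 10.28 | 85.1% | 11.49 | 76.5% | 55 | 0.63 |
| Role-Emotional | 15 | 14.94 | 80.3% | 16.70 | 71.1% | 62 | 0.68 |
| Mental Health | 9 | 8.15 | 87.2% | 9.11 | 79.0% | 52 | 0.61 |

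The change-score values round up to 6, 11, 12, 17 and 10, which is not the plan's table.

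**At the planned number of completers.** 115 × 0.85 = 97.75, about 49 per arm. Change-score power is then 78.2, 74.2, 75.6, 70.2 and 78.2%, in the table's order.

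**Range over r, 50 per arm.** Change-score power runs from 61% to 70% at r = 0.5 and from 83% to 89% at r = 0.7. The observed r is not in the documents.

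**Precision.** The ratio of interval widths, change to ANCOVA, is √[2(1 − r)/(1 − r²)] = √[2/(1 + r)]. It is 1.155 at r = 0.5, 1.118 at 0.6 and 1.085 at 0.7.

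**Sidedness check.** One-sided ANCOVA gives 4.01, 8.41, 9.09, 13.22 and 7.21, rounding up to 5, 9, 10, 14 and 8, which does not match. A one-sided test of change gives 4.48, 9.41, 10.17, 14.78 and 8.06, which does round up to the table.

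**The original mixed model.** It was to use scores from randomization onward, and the section Method for Assigning Subjects to Groups places the baseline survey before randomization. If baseline is left out, the mean of days 60 and 90 has factor (1 + r)/2 = 0.80, the same as the change score, and the same power. If baseline is included as a covariate, the factor is 0.80 − 0.36 = 0.44 and power is 96, 94, 95, 92 and 96%. These two figures assume equal correlation between all visits. Neither factor is the 0.64 behind the table, so the amendment did not create the mismatch alone.

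**The case against.** - **The gap is small for some scales.** This stands for MCS and Mental Health: about one point of power, and 5.06 against 5 or 9.11 against 9 is rounding distance. It does not stand for Role-Emotional (16.7 against 15), nor for the power of Vitality and Social Functioning, at 75% and 76%.
- **The result depends on an assumed r.** It does: at r = 0.7 every scale exceeds 80%, and at 0.5 every scale is further short. But 0.60 is the plan's own value, and the power claim has to hold there.
- **The plan may have meant a one-sided test of change.** That reading fits the rounded table, and the Accrual section does speak of change. However, it names ANCOVA and quotes r², the quantity ANCOVA uses, and nothing in the documents declares a one-sided test.
- **The amendment was reasoned, and nothing changed.** The amendment cites covariate balance and small therapist clusters, and says it preceded unblinding and access to outcome data. That supports keeping the primary as it is. Balance does not, however, recover the precision that baseline adjustment would give. Agreement with the mixed model may not bear on the point, because the documents do not say whether baseline SF-36 was in that model. Similar observed results also do not correct a stated power figure.
- **The trial is complete, so restating power alters no estimate.** True. It alters only what a reader may conclude about the sensitivity of the declared test.
- **The original model's lack of baseline SF-36 is inferred.** Fair: the text is unclear, and the two factors shown for it are scenarios. The main finding does not need them.

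**Conclusion.** The concern holds. The power statement does not describe the declared primary test. At r = 0.60, two-sided 0.05 and 50 per arm, that test falls about 1 point short of 80% for MCS and Mental Health, 5 points for Vitality, between 3 and 4 points for Social Functioning, and 9 points for Role-Emotional. This rests on the two-sample reading of the paired test, equal variances over time and the plan's own correlation.

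The comparison of change is unbiased under randomization, and no changed conclusion is shown. The fault lies in the stated sensitivity and in forgone precision. It should be fixed, but it does not undermine the trial.

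**What to change.** 1. Restate the detectable differences for the primary test used, giving r, sidedness and the number analysed. Two-sided at r = 0.60 they are about 5.1, 10.6, 11.5, 16.7 and 9.1 at 50 per arm. At about 49 per arm they are 5.1, 10.7, 11.6, 16.9 and 9.2.
2. Describe the primary as a two-sample t-test comparing change from baseline to day 60 between arms. If something else was done, say what.
3. Keep that test as primary, since it is stated to have been fixed before unblinding. Add one supportive analysis, labelled post hoc: the between-arm contrast in day-60 SF-36 with baseline SF-36 as a fixed covariate, whatever the observed balance.
4. State whether baseline SF-36 was in the fitted mixed model, so that readers know what its agreement with the t-test covers.

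The cost is some rewording and one extra model on data already held, with no further patients or visits. The stated detectable differences become slightly less favourable, and the post hoc label limits the weight that the adjusted result can carry.
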